8.3.4.1. Grading Scales

The grading scales used in this study to assess local reactions and systemic events as described below are derived from the FDA CBER guidelines on toxicity grading scales for healthy adult and adolescent volunteers enrolled in preventive vaccine clinical trials, ²⁶ with adaptations for applicability to healthy younger children.

8.3.4.2. Local Reactions

During the reactogenicity e-diary reporting period, participants or participants' parents/legal guardians will be asked to assess redness, swelling, and pain at the injection site and to record the symptoms in the reactogenicity e-diary daily for 7 days (Days 1 through 7) after each vaccination. If a local reaction persists beyond the end of the reactogenicity e-diary period following vaccination, the participant or participant's parent(s)/legal guardian will be requested to report that information. The investigator will enter this additional information in the CRF.

Participants will be provided with a measuring device. Redness and swelling will be measured and recorded in caliper units (measuring device units; range: 1 to 14 caliper units for participants \geq 2 to <12 years of age and 1 to 21 caliper units for participants \geq 12 to 18 years of age) for the first 7 days following vaccination (Days 1 through 7), and then categorized as absent, mild, moderate, or severe using the scale shown in Table 2. Measuring device units can be converted to centimeters according to the following formula: 1 measuring device unit = 0.5 cm. Pain at the injection site will be assessed by the participants or participants' parent(s)/legal guardians as absent, mild, moderate, or severe according to the grading scale in Table 2.

If a Grade 3 local reaction is reported in the reactogenicity e-diary (redness or swelling >14 caliper units for participants <12 years of age or >20 caliper units for participants ≥12 years of age; Grade 3 pain at the injection site), a telephone contact should occur to ascertain further details and determine whether a site visit is clinically indicated. Only an investigator or medically qualified person is able to classify a participant's local reaction as Grade 4. If a participant experiences a confirmed Grade 4 local reaction, the investigator must immediately notify the sponsor and, if it is determined to be related to the administration of the study intervention, further vaccinations (if applicable) will be discontinued in that participant.

1 40010 21	Event Henricon Graning Senie				
	Participant Age	Mild (Grade 1)	Moderate (Grade 2)	Severe ^a (Grade 3)	Potentially Life-Threatening ^b (Grade 4)
Pain at the injection site	≥2 Years	Does not interfere with activity	Interferes with activity	Prevents daily activity	Emergency room visit or hospitalization for severe pain at the injection site
Redness	≥2 Years to <12 years	1 to 4 caliper units (or measuring device units) = 0.5 to 2.0 cm	5 to 14 caliper units (or measuring device units) = >2.0 to 7.0 cm	>14 caliper units (or measuring device units) = >7 cm	Necrosis or exfoliative dermatitis
	≥12 Years	5 to 10 caliper units (or measuring device units) = >2.0 to 5.0 cm	11 to 20 caliper units (or measuring device units) = >5.0 to 10.0 cm	>20 caliper units (or measuring device units) = >10 cm	Necrosis or exfoliative dermatitis
Swelling	≥2 Years to <12 years	1 to 4 caliper units (or measuring device units) = 0.5 to 2.0 cm	5 to 14 caliper units (or measuring device units) = >2.0 to 7.0 cm	>14 caliper units (or measuring device units) = >7 cm	Necrosis
	≥12 Years	5 to 10 caliper units (measuring device units) = >2.0 cm to 5.0 cm	11 to 20 caliper units (measuring device units) = >5.0 cm to 10.0 cm	>20 caliper units (or measuring device units) =>10 cm	Necrosis

Table 2. Local Reaction Grading Scale

- a. Parent(s)/legal guardians of participants <12 years of age experiencing local reactions >14 caliper units (>7 cm), participants or parent(s)/legal guardians of participants ≥12 years of age experiencing local reactions >20 caliper units (>10 cm), and parent(s)/legal guardians of participants experiencing Grade 3 pain at the injection site are to be contacted by the study site. An unscheduled visit may be required.
- b. Only an investigator or qualified designee is able to classify a participant's local reaction as Grade 4, after clinical evaluation of the participant or documentation from another medically qualified source (eg, emergency room or hospital record). Grade 4 local reactions will be collected on the AE CRF and assessed by the investigator using the AE intensity grading scale as detailed in Section 10.2.3.

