4.1.2. Intervention Groups and Duration

Dose finding will begin with 120 μg of RSVpreF in participants 5 to <18 years of age. The IRC will review safety data (e-diary and AEs) acquired up to 7 days after dose administration once a minimum of 10 and up to approximately 40 participants have been vaccinated. Upon confirmation of an acceptable safety assessment by the IRC, dose administration may commence with 60 μg in participants 2 to <5 years of age. The same process with an IRC review of safety data (e-diary and AEs) acquired up to 7 days after dose administration at the low-dose level from participants 2 to <5 years of age will be followed before administering the 120- μg dose to this younger stratum.

In the 2- to <5-year age stratum, if $60 \mu g$ is considered unacceptable based on the safety assessment, administration of the 120- μg dose level will not commence. In this case, an optional lower dose level may commence. Upon IRC review, RSVpreF $60 \mu g$ may also be given to participants in the 5- to <18-year age stratum.

Duration: The study duration for each participant will be approximately 6 months.

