8.3.4. Reactogenicity Electronic Diary

The participant or participant's parent(s)/legal guardian will be required to complete a reactogenicity e-diary after each vaccination. These participants or participants' parent(s)/legal guardians will be asked to monitor and record local reactions, systemic events, and temperature for 7 days from the day of administration of the study intervention. The reactogenicity e-diary allows recording of these assessments only within a fixed time window, thus providing an accurate representation of the participant's experience at that time. Data on local reactions and systemic events reported in the reactogenicity e-diary will be transferred electronically to a third-party vendor, where they will be continually available for review by investigators, Pfizer clinicians, and other selected study team members via an internet-based portal.

At intervals agreed to by the vendor and Pfizer, these data will be transferred electronically into Pfizer's database for analysis and reporting. These data do not need to be reported by the investigator in the CRF as AEs.

Investigators (or designee) will be required to review the reactogenicity e-diary data online at frequent intervals as part of the ongoing safety review.

The investigator or designee must obtain stop dates from the participant or participant's parent(s)/legal guardian for any reactions ongoing on the last day that the reactogenicity e-diary was completed. The stop dates should be documented in the source documents and the information entered in the CRF.

Please note that all provisioned e-diary devices must be collected at the end of Visit 3 (1-month follow-up visit) per the SoA.

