- Ask the participant's parent(s)/legal guardian, as appropriate, to contact the site staff or investigator immediately if the participant experiences any of the following from Day 1 through Day 7 after vaccination (where Day 1 is the day of vaccination) to determine if an unscheduled reactogenicity visit is required:
 - Fever $\ge 39.0^{\circ}\text{C} (>102.1^{\circ}\text{F}).$
 - Redness or swelling at the injection site >14 caliper units (or >7 cm) for children <12 years old and/or >20 caliper units (or >10 cm) for children ≥12 years old.
 - Grade 3 pain at the injection site.
 - Any severe systemic event.
 - If the participant doesn't call, the site should contact the participant to determine if an unscheduled reactogenicity visit is required.
- Record AEs, SAEs, AESIs, and NDCMCs as described in Section 8.4.
- Ask the participant's parent(s)/legal guardian to contact the site staff or investigator immediately if a medically attended event (eg, doctor's visit, emergency room visit) or hospitalization occurs.
- Schedule an appointment for the participant's next study visit.
- Complete the source documents.
- The investigator or an authorized designee completes the CRFs and the dispenser/administrator completes the study intervention accountability records.
- The investigator or appropriately qualified designee reviews the reactogenicity e-diary data online following vaccination to evaluate participant compliance and as part of the ongoing safety review. Daily review is optimal during the active diary period.

8.10.2. Visit 2 – 1-Week Follow-Up Visit (Telehealth; 6 to 8 Days After Vaccination on Day 1)

- Contact the participant's parent(s)/legal guardian by telephone.
- Obtain details of any nonstudy vaccinations and prohibited concomitant medications and treatments as described in Section 6.9.

- Review the participant's reactogenicity e-diary data. Collect stop dates of any reactogenicity e-diary events ongoing on the last day that the reactogenicity e-diary was completed and record stop dates in the CRF if required.
- Record AEs, SAEs, AESIs, and NDCMCs as described in Section 8.4.
- Schedule an appointment for the participant's next study visit.
- Remind the participant's parent(s)/legal guardian to bring the e-diary to the next visit.
- Complete the source documents.
- The investigator or an authorized designee completes the CRFs.

8.10.3. Visit 3 – 1-Month Follow-Up Visit (Clinic; 28 to 35 Days After Visit 1)

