If a participant or participant's parent(s)/legal guardian reports redness or swelling >14 caliper units (or >7 cm) for participants <12 years of age and >20 caliper units (or >10 cm) for participants ≥12 years of age or a Grade 3 local reaction (Table 2), any Grade 3 systemic event (Table 3), or fever >39.0°C (102.1°F) (Table 4) in the reactogenicity e-diary, a telephone contact should occur to ascertain further details and determine whether a site visit is clinically indicated. If suspected Grade 4 local reaction (Table 2), systemic event (Table 3), or fever >40.0°C (>104.0°F) (Table 4) is reported in the reactogenicity e-diary, a telephone contact or site visit should occur to confirm whether the event meets the criteria for Grade 4. A site visit must be scheduled as soon as possible to assess the participant unless any of the following is true:

- The participant is unable to attend the unscheduled visit.
- The local reaction/systemic event is no longer present at the time of the telephone contact.
- The participant or participant's parent(s)/legal guardian recorded an incorrect value in the reactogenicity e-diary (confirmation of a reactogenicity e-diary data entry error).
- The PI or authorized designee determined it was not needed.
- This telephone contact (or site visit) will be recorded in the participant's source documentation and the CRF.

If the participant is unable to attend the unscheduled visit, or the PI or authorized designee determined it was not needed, any ongoing local reactions/systemic events must be assessed at the next study visit.

During the unscheduled visit, the reactions should be assessed by the investigator or a medically qualified member of the study staff such as a study physician or a study nurse, as applicable to the investigator's local practice, who will:

- Measure body temperature (°F/°C).
- Measure minimum and maximum diameters of redness (if present).
- Measure minimum and maximum diameters of swelling (if present).
- Assess injection site pain (if present) in accordance with the grades provided in Table 2.
- Assess systemic events (if present) in accordance with the grades provided in Table 3.
- Assess for other findings associated with the reaction and record on the AE page of the CRF, if appropriate.
- The investigator or an authorized designee will complete the unscheduled visit assessment page of the CRF.

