# 3. ENDPOINTS AND BASELINE VARIABLES: DEFINITIONS AND CONVENTIONS

## 3.1. Primary Endpoint(s)

#### 3.1.1. Primary Safety Endpoints

Primary safety endpoints include both reactogenicity data collected from the e-diary and AE data collected from the CRF.

Based on feedback from the FDA on multiple vaccine programs, reactogenicity data will utilize both e-diary data (prompted local reactions and systemic events) and reactogenicity events (related or unrelated) reported in the AE CRF during the e-diary collection period. Since the AE CRF does not designate a specific page to collect reactogenicity data for an untransmitted e-diary, Pfizer has adopted a process of providing a listing of AEs reported within 7 days after vaccination to the clinical team to review and determine ("flag") which

PTs should be considered reactogenicity events before the database lock. AEs reported on the same day of vaccination but missing a start time are defaulted to AEs reported after vaccination. Following these review steps, those AEs reported within 7 days after vaccination that match flagged PTs (either related or unrelated) will be considered reactogenicity data. If the same reactogenicity event is reported on the same day from both the e-diary and the AE CRF, the highest grade from the 2 data sources will be used for that specific day for analysis.

It should be noted that the data collection in the AE CRF is different from that of the e-diary:

- For redness, swelling, and fever, the measured size of redness and swelling at the injection site and temperature are recorded in the e-diary, but not in the AE CRF. As the missing e-diary entries are monitored with ongoing review of the prompted reactions reported in the AE CRF, any measurement recorded in the query response will be taken into consideration for the primary analysis using the data handling memo for analysis purposes. For the 7 days, only the maximum grading from both sources will be used for the aggregated severity analysis.
- For pain at the injection site and all other systemic events, the severity grading algorithm for the e-diary data and the AE CRF may not be the same. Pfizer will choose the highest-severity grade.

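### Below age 12, the stated recording range for redness and swelling (1 to 14 caliper units) stops at the top of Grade 2, so it contains no Grade 3 value

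*Protocol*

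**What the plan says.** Protocol Section 8.3.4.2 has redness and swelling measured and recorded in caliper units over Days 1 to 7 and then graded with Table 2. The stated scale is "range: 1 to 14 caliper units for participants" aged 2 to <12 years, and 1 to 21 units from 12 years; one unit is 0.5 cm.

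For ages 2 to <12, Table 2 gives Grade 1 as 1 to 4 units, Grade 2 as 5 to 14 units, and Grade 3 as ">14 caliper units (or measuring device units) = >7 cm". From 12 years, Grade 3 is above 20 units (10 cm).

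Several places rely on values above 14 in children under 12:

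- Section 8.3.4.2, next paragraph: a telephone contact follows an e-diary report of "redness or swelling >14 caliper units for participants <12 years of age or >20 caliper units for participants" aged 12 and over. Table 2 footnote a uses the same limits.
- Section 8.10.1: parents are asked to call the site for "Redness or swelling at the injection site >14 caliper units (or >7 cm) for children <12 years old".
- Section 8.11: the telephone contact applies when the family "reports redness or swelling >14 caliper units (or >7 cm) for participants <12 years of age" in the e-diary.

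On use of the data, Section 4.1.2 states: "The IRC will review safety data (e-diary and AEs) acquired up to 7 days after dose administration". Protocol Table 5 presents local reactions by maximum severity as part of the primary endpoint analysis.

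**The concern.** A scale that is recorded first and graded afterwards must contain at least one value in every size-based grade. The older range does; the younger one does not. The older range, with one value beyond its threshold, suggests that the same was meant for the younger children.

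If the e-diary was built to the stated range, a reaction larger than 7 cm in a child under 12 would be entered as at most 14 units and graded moderate. The e-diary contact trigger for values above 14 could not fire. The IRC would then see no severe redness or swelling in the e-diary data it reviews before the 120 µg dose is given to 2- to <5-year-olds. In the SAP's e-diary-only analysis of maximum severity (Section 6.1.1.3), those rates would be zero by construction.

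The effect is limited to the Grade 2/3 split for redness and swelling. Pain and systemic events do not use this scale. Grade 4 redness and swelling are not defined by size. Stopping rule 4 already excludes local reactions on Days 1 to 7.

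**Working it through.** **Step 1. Place every recordable value in its grade.** Inputs: the ranges and the conversion of 1 unit = 0.5 cm from Protocol Section 8.3.4.2, and the grades from Table 2.

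| | 2 to <12 years | 12 years and over |
|---|---|---|
| Stated recording range | 1 to 14 | 1 to 21 |
| Values in Grade 1 | 1 to 4 | 5 to 10 |
| Values in Grade 2 | 5 to 14 | 11 to 20 |
| Values in Grade 3 | none | 21 |
| Top of range in cm | 14 × 0.5 = 7.0 | 21 × 0.5 = 10.5 |
| Grade 3 starts above | 14 × 0.5 = 7.0 cm | 20 × 0.5 = 10.0 cm |

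The centimetre figures in Table 2 agree with the conversion, so the mismatch lies between the range and the grades. The smallest Grade 3 value below age 12 is 15 units (7.5 cm), which is outside the stated range.

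**Step 2. Share of participants on the younger scale.** Inputs: 20 or 40 participants aged 2 to <5 and 40 or 80 aged 5 to <18, for totals of 60 or 120 (Protocol Section 4.1.1). The age split within 5 to <18 is not stated.

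- Minimum, with nobody in the older stratum under 12: 20/60 = 40/120 = 33%.
- Maximum, with everyone in the older stratum under 12: 60/60 = 120/120 = 100%.
- Uniform ages over 5 to <18 (assumption; 7 of the 13 years lie below 12): (20 + 40 × 7/13)/60 = 41.5/60 = 69%, or (40 + 80 × 7/13)/120 = 83.1/120 = 69%.

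These shares count children measured on the scale. They do not count children with reactions above 7 cm, for which the documents give no rate.

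**Step 3. What a capped e-diary would report at 2 to <5 years.** Assume a cap at 14 and 20 transmitted diaries per dose. The e-diary-only count of severe redness, and of severe swelling, is then 0/20 at each dose. The Clopper-Pearson upper limit for 0/n is 1 − 0.025^(1/n); with n = 20, 1 − 0.025^(1/20) = 16.8%. The interval 0 to 16.8% would be printed whether the true rate were 0% or 50%.

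**Step 4. Could a severe grade reach the main analysis another way?**

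- SAP Section 3.1.1 and SAP Table 4 take the higher of the e-diary and AE CRF grades. However, Protocol Section 8.3.4 says of e-diary data: "These data do not need to be reported by the investigator in the CRF as AEs". SAP Section 5.3.1.1 looks to the AE CRF to fill missed diary days, and a completed entry of 14 is not a missed day.
- An AE CRF entry would not carry the size criterion. SAP Section 3.1.1 notes that "the measured size of redness and swelling at the injection site and temperature are recorded in the e-diary, but not in the AE CRF". AE intensity in Protocol Section 10.2.3 is graded by interference with usual function, so a wide but painless area of redness could be recorded there as mild.
- At an unscheduled visit, staff measure diameters and complete a separate CRF page (Protocol Section 8.11). The SAP does not name that page as a source of the grade.

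The routes exist, but none reliably turns a reaction above 7 cm into a Grade 3 in the analysis.

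**The case against.** The strongest reply is that this may be one wrong number in a parenthesis. Nothing in the documents says that e-diary entry is capped. Sections 8.3.4.2 and 8.11 speak of values above 14 being reported in the e-diary, which suggests a build that accepts them. The range may describe the measuring device and not a field limit. This stands: the operational effect is unknown, and only the contradiction in the text is certain.

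The primary estimand is also largely protected. It is the percentage of participants reporting a local reaction, and a reaction above 7 cm entered as 14 still counts as present. That is correct, but maximum severity is part of the primary endpoint analysis and would shift.

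There are further safeguards. Parents are told to call for reactions above 7 cm, an instruction that needs no e-diary entry. The IRC also sees AEs. SAP Section 3.1.1 allows sizes given in query responses to be used, and SAP Section 6.1.1.3 presents the difference between the primary and e-diary-only results. These reduce the risk without removing it. The query-response provision concerns missing e-diary entries, and the comparison between analyses shows a discrepancy only if someone entered a severe AE.

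Finally, counting entries of 14 as Grade 3 departs from Table 2, where 14 units is Grade 2. That is fair: such an analysis is only a worst-case bound and should be labelled as one.

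**Conclusion.** The concern holds. As written, the recording range for ages 2 to <12 contains no Grade 3 value, the range from 12 years contains one, and the rest of the protocol relies on values above 14 in the younger children. Confidence in the contradiction is high.

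The practical consequence depends on the e-diary build. If values above 14 are accepted, only the text needs correcting. If entry stops at 14, e-diary Grade 3 redness and swelling is impossible for the whole 2 to <5 stratum and for everyone aged 5 to <12, and the IRC's e-diary data would understate severity in the youngest children. This should be fixed, because it affects how a primary safety measurement is recorded and costs almost nothing to settle.

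**What to change.** 1. In Protocol Section 8.3.4.2, extend the stated recording range for 2 to <12 years past 14, for example 1 to 15 with 15 meaning more than 14, as 21 serves for more than 20 in the older group. Leave the grade thresholds unchanged.
2. Reconcile Section 8.3.4.2, Table 2 with footnote a, Section 8.10.1 and Section 8.11 so that they describe the same scale.
3. Check that the e-diary field and the measuring device accept values above 14 for this age group.
4. Only if a cap at 14 is found: query entries of exactly 14 units, and add to SAP Section 6.1.1.3 a sensitivity analysis that counts unresolved ones as Grade 3, labelled as a worst-case bound.

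The cost is one number in the protocol and one check of a field limit, with no extra participants or visits. The queries and the added analysis arise only if the cap is confirmed.

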8.3.4.3. Systemic Events

During the reactogenicity e-diary reporting period, participants or participants' parent(s)/legal guardians will be asked to assess vomiting, diarrhea, headache, fatigue/tiredness, muscle pain, and joint pain and to record the symptoms in the reactogenicity e-diary. The symptoms will be assessed by the participant or participant's parent(s)/legal guardian as absent, mild, moderate, or severe according to the grading scale in Table 3.

If a Grade 3 systemic event is reported in the reactogenicity e-diary, a telephone contact should occur to ascertain further details and determine whether a site visit is clinically indicated. Only an investigator or medically qualified person is able to classify a participant's systemic event as Grade 4. If a participant experiences a confirmed Grade 4 systemic event, the investigator must immediately notify the sponsor and, if it is determined to be related to the administration of the study intervention, further vaccinations (if applicable) will be discontinued in that participant.

Table 3. Systemic Event Grading Scale for Participants ≥2 Years of Age

	Mild (Grade 1)	Moderate (Grade 2)	Severe (Grade 3)	Potentially Life-Threatening (Grade 4) ^a
Vomiting	1-2 times in 24 hours	>2 times in 24 hours	Requires IV hydration	Emergency room visit or hospitalization for severe vomiting
Diarrhea	2 to 3 loose stools in 24 hours	4 to 5 loose stools in 24 hours	6 or more loose stools in 24 hours	Emergency room visit or hospitalization for severe diarrhea
Headache	Does not interfere with activity	Some interference with activity	Prevents daily routine activity	Emergency room visit or hospitalization for severe headache
Fatigue/tiredness	Does not interfere with activity	Some interference with activity	Prevents daily routine activity	Emergency room visit or hospitalization for severe fatigue/tiredness
Muscle pain	Does not interfere with activity	Some interference with activity	Prevents daily routine activity	Emergency room visit or hospitalization for severe muscle pain
Joint pain	Does not interfere with activity	Some interference with activity	Prevents daily routine activity	Emergency room visit or hospitalization for severe joint pain

a. Only an investigator or qualified designee is able to classify a participant's systemic event as Grade 4, after clinical evaluation of the participant or documentation from another medically qualified source (eg, emergency room or hospital record). Grade 4 local reactions will be collected on the AE CRF and assessed by the investigator using the AE intensity grading scale as detailed in Section 10.2.3.

